2.2 Secondary objectives

The secondary objectives (presented in hierarchical order) of the study are to compare the effect of long-term treatment with ticagrelor vs. clopidogrel, in patients with established PAD (see definition Section 4.1) on:

- The event rate of cardiovascular death (CV Death), Myocardial infarction (MI), Ischemic Stroke, and Acute Limb Ischemia (ALI). The efficacy variable is time from randomization to first occurrence of any event in the composite of CV Death, MI, Ischemic Stroke and ALI.
- The event rate of CV death. The efficacy variable is time from randomisation to occurrence of CV death.
- The event rate of MI. The efficacy variable is time from randomisation to occurrence of MI.

- the event rate of all-cause mortality. The efficacy variable is time from randomisation to all-cause mortality.
- The event rate of CV death, MI, and all-cause stroke (ischaemic or haemorrhagic). The efficacy variable is time from randomisation to CV death, MI, and all-cause stroke (ischaemic or haemorrhagic).
- The event rate of ALI. The efficacy variable is time from randomisation to occurrence of ALI.
- The event rate of Lower Extremity Revascularization. The efficacy variable is time from randomisation to occurrence of Lower Exetremity Revascularization
- The event rate of all revascularization (coronary and periphera [limb, mesenteric, renal, carotid and other]). The efficacy variable is time from randomisation to occurrence of any revascularization

2.2.1 Other objectives

Other objectives are exploratory with the purpose of comparing other possible long-term treatment effects of ticagrelor vs. clopidogrel in patients with established PAD on:

- Net clinical benefit evaluated by
 - a) The variable is time from randomisation to first occurrence of any event in the following composite of all-cause mortality, MI, ischaemic stroke, ALI or major amputation caused by PAD, and fatal bleeding or intracranial bleeding.
 - b) The variable is time from randomisation to first occurrence of any event in the following composite of all-cause mortality, MI, ischaemic stroke, ALI or major amputation caused by PAD, and TIMI major bleeding.
- the event rate of non-CV death. The efficacy variable is time from randomisation to occurrence of non-CV death.
- the progression of the clinical/symptomatic status of the limb by changes in clinical stage (Rutherford and Fontaine stage).
- The event rate of all amputations. The efficacy variable is time from randomization to occurrence of all amputations caused by PAD
- the event rate of major amputation caused by PAD. The efficacy variable is time from randomisation to occurrence of major amputation caused by PAD.

- the impact on quality of life by collecting health related quality of life data using the Peripheral Artery Questionnaire (PAQ). The PAQ instrument will be administered at all clinics in countries where a validated form is available in local language.
- the primary efficacy and primary safety variable in subgroups of patients with established risk factors for PAD (eg, clinical stage, prior MI, diabetes, hyperlipidemia, tobacco use, etc).
- the event rate of CV-related hospitalisation (including all-cause death, MI, ischaemic stroke, lower extremity revascularisation, major amputation due to PAD, transient ischaemia attack (TIA), coronary revascularisation or unstable angina). The efficacy variable is a) total CV hospital days, and b) time from randomisation to first occurrence of any of these events. Any individual component not already evaluated will also be examined in an analogous manner.
- the within study cost consequences and the long term cost-effectiveness of ticagrelor vs. clopidogrel to support health technology assessment. Information will be collected on health care utilization associated with hospitalisations, rehabilitation and long-term care in all patients. Utilities assessed by Euro Quality of Life-5 Dimensions (EQ-5D) will be collected at all clinics in countries where a validated form is available in the local language.

2.3 Safety objective

Non-serious AEs of interest (ie, bleeding events, dyspnoea, renal impairment/increased creatinine, bradyarrhythmia, increased liver function tests [LFTs], gout/uric acid increases, pneumonia, gynecomastia, abnormal uterine bleeding, all malignancies excluding non-melanoma skin cancers), adverse events that are ongoing at the time of permanent discontinuation of study medication due to an adverse event (DAEs) and all serious adverse events (SAEs) will be reviewed within the context of the earlier safety experience with the drug. The overall safety objective of this study is to assess the safety and tolerability of long-term therapy with ticagrelor compared to clopidogrel in patients with established PAD. Bleeding events will be analyzed using the Thrombolysis in Myocardial Infarction Study Group (TIMI), PLATO, Bleeding Academic Research Consortium (BARC) and International Society of Thrombosis and Haemostasis (ISTH) definitions. Specific focus will be on:

- Time to first TIMI major bleeding event following the first dose of study medication (primary safety objective)
- Time to first TIMI major or minor bleeding event
- Time to first PLATO major bleeding event

- Time to permanent discontinuation of study medication due to any major bleeding event
- Evaluation of non-serious AEs of interest, DAEs and SAEs

3. STUDY PLAN AND PROCEDURES

This Clinical Study Protocol (CSP) has been subject to a peer review and approval by the Executive Committee and the Data Monitoring Committee according to AstraZeneca standard procedures.

3.1 Overall study design and flow chart

This is a multicentre, randomised, double blind, double-dummy, parallel group, endpoint driven phase IIIb study to assess the prevention of atherothrombotic events with ticagrelor 90 mg bd compared to clopidogrel 75 mg od in patients with established PAD. The study design is shown in Figure 1.

The study will be designed, directed and published by an Executive Committee (see Section 5.10.1.1). The following additional committees will be selected; an independent safety Data Monitoring Committee (DMC) (see Section 12.4.2), a blinded independent Clinical Event adjudication Committee (CEC) (see Section 12.4.1), an International Steering Committee (see Section 5.10.1.2), and an Operations Committee (see Section 5.10.1.3).

Duration of the study

The anticipated duration of the study is approximately 40 months, including an anticipated enrolment period of 15 months and follow-up period of 25 months. However, the actual duration of the study will be based on accrual of the predetermined number of events (1364) for the primary endpoint, and therefore the study may be shorter or longer than 40 months. Any decision to increase or decrease patient numbers or extend or shorten treatment duration will be based on blinded event rate data. The Executive Committee of the trial will monitor the aggregate blinded event rate and may change the sample size or duration of follow-up to achieve the planned target number of events, in consultation with the sponsor and, as needed, the DMC.

The study plan, including enrolment/randomisation and protocol visits, is outlined in Table 1. If it is necessary to prolong the study in order to accrue the predetermined number of the primary endpoint events, visits and assessments will continue at the same frequency (ie, every 6 months).

Enrolment and randomisation

Male and female patients 50 years of age and over with established PAD, fulfilling all of the inclusion criteria (see Section 4.1) and none of the exclusion criteria (see Section 4.2) can be randomised.

The study will enrol symptomatic patients representative of the PAD disease spectrum.

Approximately 13,500 patients at approximately 950 study centres will be randomised (1:1) to receive either ticagrelor or clopidogrel monotherapy. The sample size is based on anticipated event rates that are related to the clinical stage of the disease. In an effort to achieve an appropriate claudication to critical limb ischaemia (CLI) final distribution ratio, the Executive Committee will monitor the Fontaine class (clinical stage) (Norgren (TASC II) 2007) and primary event rates and may cap enrolment to a particular subgroup based on the overall distribution and event rates. The Executive Committee will also monitor the proportion of patients enrolled with a prior history of MI and may cap enrolment on this subgroup as well.

Protocol Visits

Patients will return approximately every 6 months as outlined in Figure 1 and Table 1, for assessment of events related to the objectives of the study including efficacy, tolerability and safety. Assessment of treatment compliance and provision of study medication will be done at these visits. When visits are performed every 6 months, phone contacts will additionally be performed at a 3-month interval in between regular visits. The Investigator/study centre personnel will record non-serious AEs of interest (if any), DAEs, SAEs (if any), suspected clinical events (if any), study medication status, and use of concomitant medication. An unscheduled visit may be conducted as a result of the phone contact (eg, to follow-up on suspected clinical events).

Unscheduled visits

Unscheduled visits or phone contacts may be performed for event follow-up or early discontinuation of study medication.

Premature Treatment Discontinuation Visit (PTDV)

Patients who prematurely and/or permanently discontinued treatment with study medication but agreed to continue protocol visits should return for a PTDV, which will be done as soon as possible but no later than 15 days after prematurely discontinuing treatment with study medication. The PTDV will assess the same factors as the ESTV, with the only difference that patients who discontinue treatment early will be eligible for a PTDV.

End of Study Treatment Visit (ESTV)

When the predetermined number of primary events is anticipated, the following will occur:

- The Primary Analysis Censoring Date (PACD) will be declared by the Executive Committee
- All centre Investigators will receive communication to complete study visits as follows:
 - All randomised patients should return for their ESTV as soon as possible but not later than 60 days after the Primary Analysis Censoring Date (PACD).

Study patients will be instructed to transition from study medication to accepted antiplatelet therapy per current practice guidelines and standards.

Study Closure Visit (SCV)

- All randomised patients should return for their SCV, 35 days \pm 5 days, after their ESTV.
- All patients who prematurely and/or permanently discontinued treatment with study medication should return for the SCV as soon as possible but not later than 60 days after the PACD.
- Patients who are not attending scheduled visits when PACD is declared will be contacted to schedule their SCV as soon as possible but not later than 60 days after PACD, for assessment of as many endpoints in the trial as possible (ie, health or vital status as per agreement at a minimum) in person, by telephone, by checking medical records or by collecting information from publicly available sources. It is strongly recommended that all patients attend their SCV in person.

For further details on procedures for discontinuing patients from study medication, refer to Section 5.8, and for the rare patient who must withdraw from study (study medication and visit assessments) refer to Section 5.9.

[figure not shown]

Figure 1 **Study Flow Chart**

dd = double dummy, db = double blind, PTDV = Premature Treatment Discontinuation Visit, PACD = Primary Analysis Censoring Date, ESTV = End of Study Treatment Visit, SCV = Study Closure Visit, od = once daily dosing, bd = twice daily dosing

- 1 Telephone follow-up will additionally be performed at a 3-month interval in between regular visits. Non-serious AEs of interest, DAEs, SAEs, suspected clinical events, study medication and concomitant medication status will be recorded. An unscheduled visit may be conducted as a result of the phone contact.
- 2 The Premature Treatment Discontinuation Visit (PTDV) is only done for patients who prematurely and/or permanently stop study medication.
- 3 The primary analysis censoring date (PACD) is time point in which the Executive Committee determines the number of events has been reached and study closure activities may begin.
- 4 The end of study treatment visit (ESTV) should occur as soon as possible but not later than 60 days after PACD.
- 5 The study closure visit (SCV) should occur within 35 days \pm 5 days from the last dose of study medication following PACD.
- 6 Study period will be approximately 18 months recruitment and an anticipated minimum of 18 months follow-up. The actual study period will be determined when the projected number of pre-specified primary events has been reached.

Table 1Study Plan

	Visit 1	Visit 2	Visit 3	Visits 4-X ^a	Premature Treatment Discontinuation Visit (PTDV)	End of Study Treatment Visit (ESTV)	Study Closure Visit (SCV)
Assessment	Enrolment ≤ 30 days prior to randomisation	Randomisation Day 0	2 months from randomisation ± 7d	6, 12, 18, 24, 30, 36 months from randomisation ± 7d	No more than 15 days from last dose of study medication ^b	Within 60 days from Primary Analysis Censoring Date (PACD) ^C	See footnote ^d
Signed Informed Consent	\checkmark						
Inclusion & Exclusion criteria	\checkmark	\checkmark					
Relevant medical and surgical history		\checkmark					
Demographics	\checkmark						
Ankle Brachial Index (ABI) or Toe Brachial Index (TBI) ^f	$\sqrt{\mathbf{e}}$	$\sqrt{\mathbf{e}}$		$\sqrt{\mathbf{e}}$	\checkmark	\checkmark	
CYP2C19 polymorphism (central lab)	\checkmark						
Electrocardiogram (ECG)		\checkmark					
Vital Signs				\checkmark	\checkmark		
Targeted Physical Examination		\checkmark					
Clinical chemistry & Haematology (local lab)						\checkmark	

	Visit 1	Visit 2	Visit 3	Visits 4-X ^a	Premature Treatment Discontinuation Visit (PTDV)	End of Study Treatment Visit (ESTV)	Study Closure Visit (SCV)
Urinalysis (local lab)	\checkmark						
Urine pregnancy test (local lab) ^g	\checkmark						
EQ-5D questionnaire		\checkmark		$\sqrt{\mathbf{h}}$	\checkmark	\checkmark	
PAQ questionnaire		\checkmark		$\sqrt{\mathbf{h}}$	\checkmark	\checkmark	
Hospitalisation information		\checkmark	\checkmark	\checkmark	\checkmark	\checkmark	
Rehabilitation information		√	\checkmark	\checkmark	\checkmark	\checkmark	
Long-term care information		√		\checkmark	\checkmark	\checkmark	
Dispense Study Medication		√	\checkmark	\checkmark			
Return Study Medication			\checkmark	\checkmark	\checkmark	\checkmark	
Compliance/ Study Medication accountability			√	V	\checkmark		
Current Medications		√		\checkmark	\checkmark	\checkmark	
Non-serious AEs of interest, DAEs, SAEs, and Endpoints	\sqrt{i}	√ ⁱ	√	\checkmark	\checkmark		

a The study is event driven and the number of visits will depend on when the pre-estimated number of primary events has been reached. If study continues > 36 months, visits will continue every six months. Telephone follow-up will additionally be performed at a 3-month interval in between regular visits.

b The Premature Treatment Discontinuation visit (PTDV) is only done for patients who prematurely and/or permanently stop study medication.

c The End of Study Treatment Visit (ESTV) should occur as soon as possible but not later than 60 days after the Primary Analysis Censoring date (PACD).

d All randomised patients should return for their SCV, 35 days ± 5 days, after their ESTV; All patients who prematurely and/or permanently discontinued treatment with study medication should return for the SCV as soon as possible but not later than 60 days after the PACD. Patients who are not attending scheduled visits when PACD is declared will be contacted to schedule their SCV as soon as possible but not later than 60 days after the PACD, for

assessment of health status or vital status as per agreement, ie, in person, by telephone, by checking medical records or by collecting information from publicly available sources. It is strongly recommended that all patients attend their SCV in person.

- e Two ABI/TBI measurements must be taken (Visit 1 and Visit 2) to determine eligibility for the study for patients enrolling under ABI criteria. One ABI/TBI measurement must be taken at Visit 1 for those entering under the revascularization criteria. For all patients, ABI is then measured at Visit 4 and ESTV. The ABI measurement at Visit 1 must be ≤ 0.80 and the ABI measurement at Visit 2 must be ≤ 0.85 . If ABI is ≥ 1.40 at Visit 1 then TBI must be taken at Visit 2 for eligibility. The TBI measurement at Visit 1 must be ≤ 0.60 and the TBI measurement at Visit 2 must be ≤ 0.65 . The measurement and limb used at V1 and V2 should be the one that is used for all subsequent visits. Subsequent measurements will occur at the 6-month visit and PTDV/ESTV. The V1 and V2 ABI/TBI measurement for the first three subjects at each site will be assessed for quality.
- f Photoplethysmographic (PPG) signal is acceptable method of assessment of TBI.
- g Only in women of child-bearing potential.
- h EQ-5D and PAQ will be collected at V2 then annually starting at the 12 month visit, and PTDV/ESTVs.
- i SAEs will be recorded from the time of informed consent, Non-serious AEs of interest, DAEs and endpoints will be collected from time of randomisation.

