12.2.3 Interim analyses

The independent DMC will perform an interim analysis for potential early termination of the study for overwhelming efficacy, additional analyses may occur as defined in the DMC Charter. This interim analysis is planned after approximately 798 primary events have been adjudicated. A one-sided significance level of 0.001 (ie approximately 3 standard errors) will be used as criterion to consider stopping the study for overwhelming benefit of ticagrelor over clopidogrel. For early stopping the one-sided p-value must be less than 0.001 for the primarv composite, as well as for CV Death alone. A one-sided significance level of 0.001 will be applied at each efficacy interim analysis. The Haybittle-Peto alpha spending function will govern the statistical testing at the final analysis to ensure an overall Type I error of 5% (East 5.2). If the planned interim analysis is performed when at least half of the total number of primary events have occurred and there are no additional interim analyses for efficacy, the significance level at the final analysis is at most 0.0494 (two-sided). If there are deviations from this plan the significance level at the final analysis will be adjusted according to the Haybittle-Peto alpha spending function. If the study is stopped at an efficacy interim analysis after having met the criteria for the primary composite endpoint and CV death, the testing of the remaining secondary endpoints will continue at the one-sided significance level 0.001. First CV death+MI+ischemic stroke+ALI will be tested and therafter variables 3-8 in the sequence described in Section 12.2.1. There will be no futility stopping rule.

The DMC charter contains more information about the DMC procedures. A copy of the treatment codes will be made available to the statistician on the DMC. The Executive Committee and AstraZeneca will not be made aware of the treatment codes until after clean file and database lock are declared. Similarly, all summary output reviewed at each DMC meeting will be held in confidence by the DMC members until the end of the study when clean file and database lock are declared. Further details are given in the DMC charter.

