12.3 Determination of sample size

Based on clinical studies and epidemiological information, the event rate for the composite of CV death, MI and ischaemic stroke was estimated to be 7% per year in a population consisting of a spectrum of symptomatic PAD patients.

In the PLATO study a 16% RRR and 1.9% ARR (ticagrelor 9.8%, clopidogrel 11.7%) at one year were observed for the endpoint of CV death, MI and stroke. In the PAD subgroup in PLATO (data on file), a similar RRR of 15% was observed at higher absolute frequencies, ARR= 2.6% (18.0% vs. 20.6%). The RRR for ticagrelor versus clopidogrel in PLATO demonstrated consistency across multiple subgroups and consistency over time during the course of PLATO. In addition, results for the endpoint CV death, MI, and ischaemic stroke were similar to those obtained for CV death, MI, and stroke. With these considerations in mind a 15% RRR, which with 7% event rate corresponds to a 1.02% ARR per year, was assumed for the primary endpoint of CV death, MI, and ischaemic stroke of this study.

Assuming a 7% annual reference event rate and a HR of 0.85 over 18 months accrual period and anticipated 18 months of minimum follow-up, randomisation of approximately 11,500 patients **was** expected to yield 1596 primary endpoint events, which provide 90% power at a 4.94% significance level. Randomising an additional 2000 patients (i.e. target randomization approximately 13500 patients) would allow us to accrue the required 1596 primary endpoint events in approximately the above time frame if the clopidogrel event rate is 6%. For definition of the significance level at the final analysis, see Section 12.2.3. The sample size

was based on a test using the logrank statistic and was calculated using nQuery Advisor^{®1} 7.0.

The observed aggregate event rate is currently estimated to be approximately 4.1%, and to conclude the study in a timely manner with maintained data quality, the number of targeted primary events will be reduced to a minimum of 1364, which will provide 85% power at 4.94% significance level. The sample size was again based on a test using the logrank statistic and was calculated using nQuery Advisor 7.0.

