12.4.2 Data Monitoring Committee

An independent Data Monitoring Committee (DMC) will be appointed and will report to the Executive Committee.

The DMC will be responsible for safeguarding the interests of the patients in the outcome study by assessing the safety of the intervention during the study, and for reviewing the overall conduct of the clinical study. The DMC will have access to the individual treatment codes and will be able to merge these with the collected study data while the study is ongoing.

The DMC charter will be prepared to detail precise roles and responsibilities and procedures to ensure maintenance of the blinding and integrity of the study in the review of accumulating data and interactions with the Executive Committee

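### Section 3.1 bases changes to sample size and duration on blinded event rates, yet allows the unblinded DMC to be consulted on them, without limiting what its advice may draw on

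*Protocol*

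**What the plan says.** The relevant statements are spread over several sections of the protocol.

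- **Section 3.1, Duration of the study.** The rule is: "Any decision to increase or decrease patient numbers or extend or shorten treatment duration will be based on blinded event rate data". Next, "The Executive Committee of the trial will monitor the aggregate blinded event rate", and that committee may alter sample size or length of follow-up so as to reach the planned number of events, "in consultation with the sponsor and, as needed, the DMC".
- **Section 12.4.2.** "The DMC will have access to the individual treatment codes and will be able to merge these with the collected study data" while the trial is running. Section 12.2.3 also gives the codes to the DMC statistician.
- **Section 12.2.3.** The Executive Committee and sponsor do not see the codes until clean file and database lock. Summary output reviewed by the DMC stays confidential until the end of the study. "This interim analysis is planned after approximately 798 primary events have been adjudicated".
- **Section 12.3.** Citing an aggregate event rate of about 4.1% and timely completion, "the number of targeted primary events will be reduced to a minimum of 1364"; the earlier target was 1596.
- **Section 12.2.4.** The Executive Committee predicts and sets the primary analysis censoring date (PACD).
- **Section 8.5.** Study procedures change only by agreement of the Executive Committee and the sponsor.
- **Section 3.** The protocol "has been subject to a peer review and approval by the Executive Committee and the Data Monitoring Committee".

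**The concern.** The Executive Committee already sees the pooled event rate. On that question, what the DMC can add is knowledge of events by arm. Section 6.4.4.1 has the DMC follow MI, ischaemic stroke and CV death, and Section 12.2.3 allows it further analyses, so it may have that knowledge at times other than the planned interim. Asking such a body whether the trial should run longer or shorter undercuts the blinded-data rule stated in the same paragraph. Agreement, objection or silence can each carry information. The confidentiality rule in Section 12.2.3 covers summary output and does not mention advice.

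Two things are at stake. One is operational: the Executive Committee, which includes sponsor members (Section 5.10.1.1), could infer the direction of the result. The other is error control. The final significance level assumes that the number of events at the final analysis does not depend on the observed treatment difference. Changing patient numbers or calendar time to reach a fixed count would not break that assumption. But 1364 is a minimum and the PACD is set by prediction, so follow-up length can still move the count.

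**Working it through.** **1. Inputs.** HR 0.85, two-sided alpha 0.0494, 1:1 allocation, 13,500 patients, targets 1596 and 1364, interim at 798 events, one-sided interim boundary 0.001 (Sections 3.1, 12.2.3, 12.3). The 4.1% rate is taken as annual. Accrual is 15 months (Section 3.1) or 18 months (note to Figure 1). Dropout is not given; 0 to 3% per year is assumed.

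**2. The plan's own figures.** Schoenfeld events = 4(z_alpha + z_beta)² / (ln HR)².
- 90% power: 4(1.965 + 1.282)² / 0.1625², which gives 1597 after rounding up.
- 85% power: 4(1.965 + 1.036)² / 0.1625², which gives 1365 after rounding up.

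The power is 89.99% at 1596 events and 84.99% at 1364. Both stated targets reproduce.

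**3. Final significance level after the cut.** The interim fraction is 798/1596 = 50.0% under the old target and 798/1364 = 58.5% under the new one. With a one-sided 0.001 boundary, the final two-sided level that keeps overall error at 5% is 0.0494 at 50.0% and 0.0496 at 58.5%. The stated 0.0494 therefore remains valid.

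**4. Does the pooled rate explain the cut?** With uniform accrual over A months, annual hazard r and no dropout, expected events at month t are N × [1 − (12/(rA)) × exp(−rt/12) × (exp(rA/12) − 1)].

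Check for A = 15, r = 0.041, t = 38.7: 13,500 × [1 − 1.0261 × 0.8761] ≈ 1364.

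| Accrual, dropout per year | 798 events | 1364 events | 1596 events |
|---|---|---|---|
| 15 months, 0% | 25.4 months | 38.7 | 44.4 |
| 15 months, 3% | 25.8 | 40.1 | 46.3 |
| 18 months, 0% | 26.9 | 40.2 | 45.9 |
| 18 months, 3% | 27.3 | 41.6 | 47.8 |

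At 4.1%, 1364 events arrive close to the planned 40 months, and 1596 arrive about six months later. The pooled rate and the timetable account for the cut.

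**5. How far follow-up moves the count.** The difference between targets is 1596 − 1364 = 232 events. Without dropout this takes 44.4 − 38.7 = 5.7 months, or about 41 events a month. With 3% dropout it takes 46.3 − 40.1 = 6.2 months, or about 37 a month. One month of follow-up is therefore worth roughly 3% of the target.

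**6. Worst case for type I error.** Suppose the choice between 1364 and 1596 were made knowing the interim statistic z at 798 events. Under the null hypothesis, the final statistic for target D given z is normal with mean z√f and variance 1 − f, where f = 798/D. Take the larger of the two conditional probabilities of exceeding ±1.965, set it to 1 where z > 3.09 (stop for benefit), and integrate over the standard normal density of z.

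- Fixed target 1364: 0.0496
- Fixed target 1596: 0.0497
- Better of the two chosen after seeing z: 0.0535

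In the direction of benefit alone the figures are 0.0249, 0.0250 and 0.0269.

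**The case against.** The strongest defence is that the bodies that decide are blinded. Section 8.5 gives changes to the Executive Committee and sponsor, and Section 12.2.3 withholds the codes from both. Section 12.4.2 leaves DMC interactions with the Executive Committee to a charter that is meant to protect the blind and is not available here. The consultation sentence concerns sample size or follow-up needed to reach the planned number of events; it does not authorise lowering that number. All of this stands, and it limits the point. It does not remove it: the protocol itself invites the consultation and puts no limit on what the advice may draw on.

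A reader might go further and infer that the cut from 1596 to 1364 was informed by the interim result. The amendment is dated 3 March 2015, which is 26.0 to 29.0 months after a Q4 2012 start. At 4.1% without dropout, about 760 to 955 events would be expected by then, against 798 for the interim, and Section 3 records DMC approval of the protocol. The document does not support that inference. The timing is a projection from uniform accrual and a constant hazard. The interim counts adjudicated events, so adjudication lag would make it later. The amended protocol still describes the interim as planned. The approval sentence names no edition and does not say that the DMC advised on the target. The stated reason is a pooled rate, and step 4 of the working bears it out.

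**Conclusion.** The point holds as a flaw in the wording of Section 3.1: a rule of blinded decision-making is followed by permission to consult an unblinded body on the same decision. It is worth correcting, but it is not evidence that an unblinded decision was made.

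Its size is modest. The extreme case is a two-sided type I error of about 0.0535 instead of 0.050, and it would require the choice of target to be driven by full knowledge of the interim statistic, which no section allows. That figure covers a choice between these two targets at 798 events only. It is not a bound on an unrestricted choice of final count, for which the protocol gives no range. The event timings rest on an annual rate of 4.1%, uniform accrual and the assumed dropout range.

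**What to change.** In Section 3.1, end the sentence after the sponsor, so that the DMC is no longer named as a party to consult. Alternatively, keep the mention and state that the DMC gives no advice drawing on unblinded data about the event target, sample size, PACD or follow-up. Either way, add that the Executive Committee and sponsor decide these matters on pooled blinded data only.

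Have the DMC informed after the decision. It needs to know the target so that the interim information fraction and, where required, the final significance level can be adjusted under Section 12.2.3. Align the DMC charter with this wording.

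The cost is a few lines of text. The Executive Committee loses a sounding board on duration; the DMC keeps its safety role and its role in stopping for efficacy.
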